## 6. Intervention protocol

## 185 6.1 Anesthesia management

- 186 6.1.1 No premedication will be administered.
- 187 6.1.2 Intraoperative monitoring includes electrocardiogram (ECG) and oxygen saturation
- 188 (SpO2) and non-invasive blood pressure.
- 189 6.1.3 All patients will undergo caesarean section under epidural anesthesia and epidural
- puncture will be performed in the left lateral decubitus position. A 16-G Tuohy needle will be
- used for puncture in the L2-3 lumbar intervertebral space. After confirming the epidural space
- by the loss-of-resistance-to-air method, a catheter will be inserted 3-4 cm in a cephalad
- 193 direction.

184

- 6.1.4 A test dose of 1.5% lidocaine 5 ml will be given. After a 5-minute observation, 0.75%
- ropivacaine 10 ml will be given, followed by an infusion of 0.75% ropivacaine at 3-5 ml/h.
- 196 6.1.5 Oxygen will be provided at 5 L·min via a face mask.
- 197 6.1.6 Study drugs will be administered when the targeted upper sensory block level was
- achieved (about 2 minutes before incision). Specifically, esketamine 0.25 mg·kg will be
- administrated intravenously over 1 min for patients in the esketamine group; the same volume
- of normal saline will be injected for patients in the control group.
- 201 6.1.7 At the end of surgery, a patient-controlled epidural analgesia will be attached for
- 202 postoperative analgesia, which is established with 0.2% ropivacaine and programmed to deliver
- a continuous infusion at 2 ml/h.

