# 251 8.1 Primary outcome

- Our co-primary outcomes include maternal pain intensity and sedation score immediately after
- fetal delivery (about 10 min after esketamine). Pain intensity will be assessed with the NRS.

- 254 Maternal sedation level will be assessed with the Ramsay Sedation Scale.
- 255 **8.2 Secondary outcomes**
- 8.2.1 Maternal pain intensity as assessed with the NRS at the following timepoints: surgical
- 257 incision (2 min after study drug administration), 5 min after study drug administration, end of
- surgery, 6 h after surgery, and 12 h after the surgery.
- 8.2.2 Maternal sedation level as assessed with the Ramsay Sedation Scale at the following
- 260 timepoints: surgical incision (2 min after study drug administration), 5 min after study drug
- administration, end of surgery, 6 h after surgery, and 12 h after the surgery.
- 262 8.2.3 Neonatal Appar score assessed at 1 and 5 minutes after birth.
- 263 8.2.4 Postnatal umbilical vein blood gas pH value.
- 264 8.3 Other outcomes
- 8.3.1 Mean blood pressure (MBP), heart rate (HR), and pulse oxygen saturation (SpO2)
- 266 measured before anesthesia, immediately after anesthesia, surgical incision (2 min after study
- drug administration), 5 min after study drug administration, immediately after fetal delivery
- 268 (10 min after study drug administration), end of surgery, and 1 h after surgery.
- 269 8.3.2 The requirement of neonatal ward admission and length of hospital stay.
- 270 8.3.3 Plasma concentrations of esketamine in maternal blood, neonatal umbilical venous blood
- and umbilical arterial blood after birth.

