# 273 **9. Adverse events**

**9.1 Definition** 

- 275 An adverse event indicates any unpredictable, unfavorable medical event that is associated with
- any medical intervention and occurs during the study period. It can be related to the study
- 277 intervention or otherwise. It can manifest as any uncomfortable signs (including abnormal
- 278 laboratory findings), symptoms, or transient morbidity.
- 279 9.2 Predicted adverse events in this study
- 9.2.1 Hypotension was defined as systolic pressure decrease <20% of baseline.
- 9.2.2 Hypertension was defined as systolic pressure increase >20% of baseline.
- 9.2.3 Bradycardia was defined as heart rate <60 bpm.
- 283 9.2.4 Tachycardia was defined as heart rate >100 bpm.
- 9.2.5 Desaturation was defined as oxygen saturation <90%.
- 285 9.2.6 Nausea and vomiting.
- 286 9.2.7 Neurological and mental signs and symptoms (such as lethargy, diplopia, dizziness,
- 287 headache, nightmare, hallucination, anxiety, and irritability) and nystagmus.

288 9.2.8 Adverse events will be managed according to routine practice.

289

290

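### The only pre-specified respiratory event is SpO2 below 90%, in women given mask oxygen, so a null desaturation comparison would say little about ventilation

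*Combined protocol and SAP*

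**What the plan says.** - **Oxygen.** Protocol 6.1.5: "Oxygen will be provided at 5 L" per minute, by face mask. It applies to both arms and does not depend on saturation. No start, stop or duration is given.
- **Monitoring.** Protocol 6.1.2: "Intraoperative monitoring includes electrocardiogram (ECG) and oxygen saturation", plus non-invasive blood pressure. Respiratory rate and capnography are not listed.
- **Respiratory event.** Protocol 9.2.5: "Desaturation was defined as oxygen saturation <90" per cent, with no duration and no other respiratory criterion.
- **SpO2 as an outcome.** Protocol 8.3.1 and SAP 3.3.1 list "Mean blood pressure (MBP), heart rate (HR), and pulse oxygen saturation (SpO2") at seven times. Three of these lie between study drug and delivery: 2 min, 5 min and about 10 min.
- **Sedation.** Protocol 8.1: "Maternal sedation level will be assessed with the Ramsay Sedation Scale". This is a co-primary outcome, on a scale that runs to deep sleep without response.
- **Other listed events.** Protocol 9.2.7: "Neurological and mental signs and symptoms (such as lethargy, diplopia, dizziness" and similar. The item covers neurological and mental signs and names no breathing or airway event.
- **Safety analysis.** Protocol 13.6 and SAP 4.6 compare the rates of adverse events, their management, or both, by chi-square or Fisher test.

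**The concern.** The trial gives an intravenous drug before delivery and measures sedation closely, but it has no direct measure of ventilation. The one respiratory event is defined on a signal that supplemental oxygen supports. If breathing became shallow or slow in some women, saturation could stay above 90% and 9.2.5 would not be met. The same holds if staff opened the airway or raised the oxygen flow before saturation fell that far.

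Oxygen blunts the signal in both arms, but any under-counting falls mainly where there are events to count. The desaturation comparison therefore leans toward no difference. The protocol background itself describes the safety of intravenous esketamine before childbirth as unclear, and the evidence on respiration that it cites is pre-clinical. At stake is how much weight a null row in the adverse-event table can bear.

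**Working it through.** The plan gives no figure on this point, so there is none to reproduce. The check has three parts.

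**1. What is collected.** I read the monitoring, data-collection, outcome, adverse-event and safety-analysis sections of the protocol and SAP for any respiratory item other than SpO2.
- Respiratory rate, apnoea, airway support and increases in oxygen flow appear in none of them.
- The maternal arterial sample in 7.2.6 is for drug concentration, in selected esketamine-arm women only. It gives no PaCO2 and no control comparison.
- Umbilical vein pH (8.2.4) is a neonatal measure.
- The Ramsay score grades responsiveness, not ventilation.

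Absence from Section 7 alone would prove little, because Section 7 also omits SpO2, heart rate and umbilical pH, which are outcomes elsewhere. The relevant absence is from Sections 8 and 9.2.

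**2. How far ventilation must fall before 9.2.5 is met.** The documents give neither an inspired oxygen fraction (FiO2) nor an alveolar-arterial gap, so both are assumed. Other assumptions are barometric pressure 760 mmHg less 47 for water vapour (713), respiratory quotient 0.8, and SpO2 90% taken as PaO2 60 mmHg. The alveolar gas equation, rearranged, is

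PaCO2 = 0.8 × (FiO2 × 713 − 60 − gap)

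| FiO2 | Gap (mmHg) | Calculation | PaCO2 at SpO2 90% (mmHg) |
|---|---|---|---|
| 0.21 (room air) | 15 | 0.8 × (149.7 − 75) | 59.8 |
| 0.35 | 50 | 0.8 × (249.6 − 110) | 111.6 |
| 0.35 | 30 | 0.8 × (249.6 − 90) | 127.6 |
| 0.40 | 50 | 0.8 × (285.2 − 110) | 140.2 |
| 0.40 | 30 | 0.8 × (285.2 − 90) | 156.2 |

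Less favourable inputs narrow the contrast but do not remove it:
- FiO2 0.30 with gap 50: 0.8 × (213.9 − 110) = 83.1 mmHg.
- FiO2 0.35 with gap 50 and the PaO2 cut-off raised to 80, to allow for a shifted saturation curve: 0.8 × (249.6 − 130) = 95.6 mmHg.
- A standard saturation curve in place of the fixed cut-off, with gaps of 10-30: about 49-65 mmHg on room air, against about 101-231 mmHg for FiO2 0.30-0.50.

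**3. What incomplete capture does to the comparison.** This is an illustration only; the event rates and capture fractions are assumptions. Take 300 women per arm (protocol 3.2), true hypoventilation rates of 5% and 0.5%, two-sided alpha 0.05, and the same capture fraction in both arms. With p1 and p2 the counted rates and p̄ their mean,

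power = Φ{[|p1 − p2| − 1.96 √(2p̄(1 − p̄)/300)] / √[(p1(1 − p1) + p2(1 − p2))/300]}

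| Share of events captured | Expected count, esketamine arm | Power |
|---|---|---|
| 100% | 300 × 0.05 = 15 | 92% |
| 50% | 7.5 | 66% |
| 20% | 3 | 32% |
| 10% | 1.5 | 18% |

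The normal approximation is rough at the smallest counts. The table shows direction, not a forecast.

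**The case against.** The strongest case on the other side has five parts.

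- **The event list is open.** Section 9.2 lists predicted events, while 9.1 covers any unfavourable sign or transient morbidity. An observed apnoea or obstruction qualifies, and 13.6 can compare both the event and its management. This stands. A reader might infer that respiratory events would go uncounted, but the documents do not support that. They support only that such events would not be prompted, defined or recorded uniformly across centres.
- **SpO2 is also an outcome in its own right.** A shift between arms above 90% could be seen at the 8.3.1 times. This stands in part: those readings are damped wherever oxygen is running, and they miss what happens between them.
- **Oxygen is not said to run throughout.** Section 6.1.5 gives a flow and a device only, so the readings before anesthesia and 1 h after surgery may or may not be on oxygen. This stands.
- **The gas equation is a steady-state relation on assumed inputs.** The drug is one injection over 1 min, with delivery about 10 min later. The equation does not cover apnoea or obstruction, either of which can still cause desaturation, and it says nothing about how often hypoventilation occurs. This stands, so it is an illustration of insensitivity and not a count of missed events.
- **No respiratory-safety hypothesis, margin or conclusion is planned.** The stated purpose is sedative and analgesic effect. This stands and limits the priority of the point.

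None of these supplies a measure of ventilation or a standard way to record respiratory interventions.

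**Conclusion.** The point holds as a gap in ascertainment. The plan's one pre-specified respiratory event is insensitive to hypoventilation in women on mask oxygen. Under the main assumptions it would need a PaCO2 of about 112-156 mmHg, against about 60 mmHg on room air; the harshest inputs tried bring the figure on oxygen down to about 83 mmHg. A null desaturation comparison would therefore be weak evidence about breathing.

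A reader might go further and infer that esketamine depresses breathing at this dose, that desaturation will be near zero in both arms whatever the drug does, or that the trial will claim respiratory safety. The documents support none of these. They contain no evidence of respiratory depression at the trial dose, no predicted event rate and no planned safety claim. The primary analyses are unaffected. Priority is optional to recommended.

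**What to change.** Changes to data collection and reporting only; none to oxygen treatment or any clinical rule:

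1. Add respiratory rate to 8.3.1 (SAP 3.3.1) at the existing time points.
2. Add three solicited events to 9.2: apnoea; any airway manoeuvre or assisted ventilation; and any increase in oxygen flow above that in 6.1.5. The trial team should define each on the case report form, record it the same way in both arms, and compare it under 13.6 (SAP 4.6). These items matter more than respiratory rate, which at fixed times shares the blind spot of SpO2 between readings.
3. Report the lowest intraoperative SpO2 by arm.
4. State in the report which SpO2 readings were taken on supplemental oxygen.

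The cost is a few form fields filled from routine monitoring or observation by staff already present, with no extra procedure. The downside is a slightly longer intraoperative form and an event table that may look less favourable.

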#### 10. Severe adverse events

# 291 **10.1 Definition**

- 292 A severe adverse event indicates any unpredictable medical events that lead to death, threat of
- 293 life, prolonged length of hospital stays, persistent disability or dysfunction, or other severe
- event.

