# 298 10.3 Record and report

- 299 10.3.1 In case of any severe adverse event, apart from active treatment and record as above,
- 300 the principal investigator and the Ethics Committee will be informed within 24 hours in written
- 301 report.
- 302 10.3.2 In case of study intervention related death, immediately stop the clinical trial, report the
- event to the Ethics Committee as soon as possible, record in detail and carefully preserve the
- 304 related documents.
- 305 10.3.3 Any severe adverse event must be followed up until it is completely resolved or when
- 306 therapy is ended.

307

308

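### The adverse and severe adverse event definitions require an event to be unpredictable, which contradicts the protocol's own list of predicted adverse events and leaves 24-hour reporting of serious listed events open to interpretation

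*Combined protocol and SAP*

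**What the plan says.** Protocol section 10.1 gives the definition: "A severe adverse event indicates any unpredictable medical events that lead to death, threat of" / "life, prolonged length of hospital stays, persistent disability or dysfunction, or other severe" event. The condition of being unpredictable stands at the front and governs every outcome that follows, including the residual category at the end.

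Section 9.1 uses the same condition for ordinary adverse events: "An adverse event indicates any unpredictable, unfavorable medical event that is associated with" any medical intervention. Section 9.2 is then headed "Predicted adverse events in this study". Items 9.2.1 to 9.2.7 list seven types: hypotension, hypertension, bradycardia, tachycardia, desaturation, nausea and vomiting, and a group of neurological and mental signs that includes hallucination and lethargy.

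Once an event is a severe adverse event, section 10.3.1 requires that "the principal investigator and the Ethics Committee will be informed within 24 hours in written" form. Section 10.3.3 requires follow-up until resolution or the end of therapy. Section 14.2.4.7 requires source inspection of every severe adverse event. The safety analysis (protocol 13.6, SAP 4.6.3) describes their occurrence.

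**The concern.** Seriousness is about what an event leads to. Expectedness is about whether its type was foreseen. Section 10.1 makes the first depend on the second. The types named in 9.2 are those the investigators have already foreseen, so the wording puts in doubt exactly the events for which the protocol should have a clear rule.

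What is at stake is mainly reporting during the trial. A center that takes 10.1 at its word could record a life-threatening desaturation as an ordinary adverse event and send no expedited report. Another center could report the same event within 24 hours. This is a multi-center trial, and its Background section says that the safety of intravenous esketamine before childbirth is still unclear, so uneven reporting of this kind matters. Reclassifying events at the end of the study would correct the summary, but it could not restore a timely report.

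**Working it through.** No arithmetic applies. The plan states no figure on this point and gives no expected rate of adverse or severe adverse events. The check sets the sections side by side.

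1. **Does 10.1, taken literally, exclude a listed type?** Take desaturation, which item 9.2.5 defines: "Desaturation was defined as oxygen saturation <90" percent. It stands under a heading that calls it predicted. Section 10.1 asks for an event that is unpredictable and leads to one of the named outcomes. A life-threatening desaturation meets the outcome part and, on the plain words, fails the first part.

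2. **Does the residual category rescue it?** No. The closing clause of 10.1, on other severe events, sits under the same opening condition.

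3. **Does another section bring it in?** No. Nothing in sections 9, 10, 13.6, 14.2 or 16, or in SAP 4.6, says that a 9.2 event becomes a severe adverse event when it reaches a 10.1 outcome.

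4. **Does the protocol itself use the word to exclude?** Not consistently. Section 9.1 attaches the word to adverse events in general, and 9.2 then classes predicted types as adverse events. The express list settles the matter for ordinary adverse events. No such list settles it for 10.1.

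5. **What depends on the label?**
   - the written report within 24 hours (10.3.1);
   - follow-up to resolution or end of therapy (10.3.3);
   - source inspection of all such events (14.2.4.7), against at least 5% of participants for original data in general (14.2.4.6);
   - the descriptive summary (13.6, SAP 4.6.3);
   - the responses in 10.2 and 16.1, which are also written in terms of severe adverse events.

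6. **What does not depend on it?**
   - The between-group test in 13.6 and SAP 4.6.4 is for adverse event rates and their management. Listed types count there whatever their severity.
   - Intervention-related death has its own rule in 10.3.2, with no condition on predictability: "In case of study intervention related death, immediately stop the clinical trial, report the" event to the Ethics Committee.
   - Interruption of the study for a severe safety problem (4.5.1) does not use the label.
   - Length of stay and neonatal ward admission are outcomes in their own right (8.3.2) and are compared between arms (13.5.2).

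What remains exposed is the non-fatal event of a listed type that meets a 10.1 outcome: its expedited report, its follow-up, its source inspection and its place in the descriptive summary.

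**The case against.** The strongest reply is that the investigators plainly do not mean the word as an exclusion. If they did, nothing in 9.2 could be an adverse event and section 9 would contradict itself. The reading that makes sense of section 9 is that the word does not bar listed types, and 10.1 can be read in the same way. No sentence says that a predicted event cannot be a severe adverse event. This stands to the extent that a reader who infers a certain exclusion goes further than the text. It does not remove the problem: 9.2 overrides the word for ordinary adverse events by listing them, and nothing does so for 10.1. Each center would have to work out the intention for itself.

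A second reply is that other routes catch much of what might be lost: the separate rule for intervention-related death, interruption for a severe safety problem, collection of maternal psychiatric symptoms (7.3.2), and length of stay as an outcome. This also stands, and it narrows the point. None of these routes replaces the 24-hour report for a non-fatal listed event.

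A third reply is that rewording is not free of consequences, because 10.2 and 16.1 act on the same label. That is correct, and the fix has to take it into account.

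**Conclusion.** The definitions in 9.1 and 10.1 contradict 9.2 and should be corrected. The result is ambiguity about whether a serious, non-fatal event of a listed type receives expedited reporting, follow-up and full source inspection, together with a possible under-count in the descriptive summary of severe adverse events. The conclusion rests on the literal wording and on the absence of any sentence linking 9.2 to 10.1. It assumes only that some centers might apply the wording as written.

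The size cannot be given. The documents contain no adverse event or severe adverse event rates, so any percentage of lost events would be invented.

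A reader might infer three stronger conclusions that the documents do not support:

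- *A biased comparison of severe adverse events between arms.* No such test is named. These events are only described, and listed types stay in the adverse event comparison.
- *A loss that falls mainly on the esketamine arm.* Section 7.3.2 allows that psychiatric symptoms may be caused by the study drugs, but no rates by arm are given, and neurological and mental signs are one of seven listed categories.
- *Deaths going unreported.* Intervention-related death is covered by 10.3.2.

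**What to change.** - Delete the word *unpredictable* from 9.1 and 10.1.
- For recording and reporting, define a severe adverse event by its outcome alone, using the outcomes already named in 10.1.
- Add one sentence saying that an event listed in 9.2 is a severe adverse event whenever it meets a 10.1 outcome.
- If expectedness is of interest, record it as a separate field on the case report form.
- Reconcile 10.2 and 16.1 with the revised definition. Both are triggered by severe adverse events, so a clearer or wider definition also changes what they apply to. The sponsor must decide how those passages should read.

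The cost is a short amendment, one extra field, and a few more 24-hour reports. Sample size, endpoints and the efficacy analysis do not change. The safety analysis in 13.6 and SAP 4.6 needs no new method, only the clearer definition.

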# 295 **10.2 Management**

- In case of any severe adverse events, the study intervention will be stopped and treatment will
- 297 be initiated immediately.

# 298 10.3 Record and report

- 299 10.3.1 In case of any severe adverse event, apart from active treatment and record as above,
- 300 the principal investigator and the Ethics Committee will be informed within 24 hours in written
- 301 report.
- 302 10.3.2 In case of study intervention related death, immediately stop the clinical trial, report the
- event to the Ethics Committee as soon as possible, record in detail and carefully preserve the
- 304 related documents.
- 305 10.3.3 Any severe adverse event must be followed up until it is completely resolved or when
- 306 therapy is ended.

307

308

# 11. The rule of unmasking

- 309 11.1 After the follow-up of all cases have been completed, the data of case report forms have
- been checked as correct, and the data entry have been finished, a database inspection report
- 311 will be written by the data manager.
- 312 11.2 After the database is locked, unmasking will be conducted. And the database will be sent
- 313 to the statisticians for statistical analysis.

314

315

# 12. Data management

- 316 12.1 The investigators should record data timely, completely and correctly according to the
- original observations and assessments.
- 318 12.2 The completed case report forms, after signed by the supervisors, will be sent to a clinical
- 319 data custodian.
- 320 12.3 After the data in the case report forms have been input and checked, the case report forms
- will be stored in sequence order.

- 322 12.4 Data management will be inspected by Clinical Research Institute of Women's Hospital
- 323 School of Medicine Zhejiang University.

325

### 13. Statistical analysis

- 326 Statistical analyses will be performed using IBM SPSS for Windows version 22.0 (IBM Corp.,
- Armonk, NY, USA) and GraphPad Prism version 5.0 (GraphPad Software Inc, San Diego, CA,
- 328 USA).

